Study participation will require participants to donate approximately 10-11 hours of their time, not including travel time. There will be a financial cost of travelling to and from Addenbrooke's for the four, weekly intervention visits but participants will be able to park at Addenbrooke's Hospital at the discounted rate of £4.80 per day which can be reimbursed. Participants will be given a token of appreciation after their participation is complete via a £10 shopping voucher.

Debrief and Communicating Results

A debriefing letter will be sent to participating dyads, thanking them for their involvement in this study and reiterating the invitation to contact the researchers about any questions or concerns that may arise after participation is complete, or if they wish to withdraw their data from the study. This letter will also include information about how the results of the study may be communicated to them.

Analysis

The focus group will be transcribed, supported by the transcription function within Microsoft Teams and reviewed by the researcher for accuracy, making amendments where required.

Qualitative focus group data will be analysed using framework Analysis (FA) (Ritchie & Spencer, 1994), with the Theoretical Framework of Acceptability (TFA) (Sekhon et al., 2017) as the framework guiding analysis. FA seeks to understand an event through five stages of analysis (Green & Thorogood, 2018) and is an increasingly popular approach in medical and health research (Gale et al., 2013). It is described as a systematic way to analyse data in a way that makes it clear how the findings of the research were obtained. This is useful to implement recommendations based on findings to guide further studies (Kiernan & Hill, 2018). This method of analysis will help to identify which theoretical constructs of acceptability are strong for this intervention and which could benefit from further attention and improvement, therefore guiding further development of the intervention.

FA will be applied as described by Green and Thorogood (2018) but using the TFA deductively. Audio data will be transcribed and read until the researcher is familiarised with the broad themes of the data. A coding key will be established using the TFA. The key will be applied to the data systematically, described as indexing. Indexed data will be charted, by

tabularising and rearranging according to thematic content in summary form. The final stage will involve mapping and interpretation to explore the relationships between the concepts connecting the TFA with the charted data; an example of this is found in Western et al.'s (2023) study on an intervention for pre-frail individuals. Some 'open coding' will also be carried out to ensure no important data are missed from the analysis (Gale et al., 2013).

In terms of quantitative data obtained from the stroke survivor participants, the degree of acceptability will be calculated by calculating the mean ratings for responses to each of the seven TFA constructs on the acceptability questionnaire measure, the mean rating for the general acceptability item (item 10), and the total mean rating of all items. For two of the seven constructs, Sekhon et al., (2022) suggest a choice of two questions, whereas all other constructs have only one question. For these two constructs, it has been decided that both of the suggested questions would be included in the acceptability questionnaire used in this study, as it was felt that the questions were different enough from one another that they would both be helpful to ask. For example, the generic TFA questionnaire suggests either 'How fair is [Intervention] for [people/ participants/ recipients] with [condition]?' or 'There are moral or ethical consequences [behaviour *i.e. to engage with*] [intervention]' as questions to measure the construct of ethicality.

To improve the sensitivity to context (Yardley, 2000) the researchers will keep reflective diaries of the data analysis process to ensure that consideration is taken of their role in the research and the analysis and to increase awareness of how this, as well as their existing knowledge, experiences and assumptions, may influence the analysis.

References

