This study will gather rich data on the acceptability of sCST for pre-frail stroke survivors to ascertain the suitability of the intervention for incorporation in the FIESTO feasibility RCT. As the study will examine the acceptability of the intervention prior to clinical trial, there will be no randomisation or control group, it is categorised as a non-randomised pilot study: a study in which “all or part of the intervention to be evaluated and other processes to be undertaken in a future trial are carried out without randomisation of participants” (Eldridge et al., 2016, p. 15).

This research will adopt a mixed methods design. Qualitative data will be collected via focus groups to gain a rich understanding of the acceptability of the intervention and how it could be changed and improved to best suit the needs and abilities of pre-frail stroke survivors from the perspective of both stroke survivors themselves and their informal carers. Descriptive quantitative data will also be collected from stroke survivors (not the informal carers) using the Theoretical Framework of Acceptability Questionnaire (Sekhon et al., 2022) to quantify acceptability, helping to highlight areas of strength or weakness in intervention acceptability. Data relating to recruitment success and group retention rates will also be collected and descriptively reported in order to determine the feasibility of recruiting participants to research using this intervention.

The philosophical stance, or paradigm, taken in this piece of research is that of pragmatism, where reality is socially constructed and, as such, it is unlikely that reality can ever be wholly understood. However, knowledge can be generated by understanding what practically works best (or doesn't work) within the specific context (Kaushik & Walsh, 2019). Due to its balanced position and practical approach, pragmatism is well suited to feasibility research (Johnson & Onwuegbuzie, 2004).

Participants

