Participants for this study will be ten dyads of adult pre-frail stroke survivors and their informal carers. The aim will be to recruit ten participants. The CST manual (Spector et al., 2020) suggested that a suitable group size for the intervention is between five and eight, however recruiting ten will allow for the possibility of group drop-out. This number is also thought to provide enough data to make meaningful conclusions about the acceptability of the intervention whilst also being a manageable number for a group intervention with two co-facilitators, thereby meeting the criteria suggested by Thabane et al. (2010). A sample size of 10 dyads is also supported by existing guidelines for qualitative analysis (Braun & Clarke, 2013). It is suggested that ten participants, divided into two focus groups of equal numbers, in line with previous research (Braun & Clarke, 2013; Guest et al., 2017) would be acceptable for this analysis.

It is planned to begin to recruit dyads when the stroke survivors are under the care of Addenbrooke's Hospital stroke services (Acute Stroke Unit and Lewin Rehabilitation Unit), participants will either be due to be discharged home or have recently been discharged home. Potential participant dyads will be identified by Addenbrooke's stroke services clinicians, who will have been fully briefed via a letter about the study and the below inclusion and exclusion criteria. Clinicians will bring the identified patients to the attention of [name] or [name], who work within the stroke services as an Honorary Consultant in Stroke Medicine and Principal Clinical Psychologist in Stroke, respectively. As [name] and [name] are members of the clinical team, they will access the stroke survivors' medical records to confirm eligibility for the research before asking the identifying clinician to provide a poster about the research and seek consent from the patient to be contacted about research by completing a 'consent to contact' form which will be uploaded onto the patients' records and uploaded to a secure online folder (password-protected and located on the UEA OneDrive for Business). The

research poster will also give potential participants the option to register their interest in the research via an online Microsoft Forms form or to email the lead researchers directly, meaning a completed 'consent to contact' form would not be required.

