Focus groups will be held via Microsoft Teams and will be recorded using the in-built record function so that they can be later transcribed ready for analysis. The groups will take place in the weeks soon after the last session of the intervention and will each last between one and two hours

The topic guides used for the informal carer and stroke survivor focus groups will each be based on the Theoretical Framework of Acceptability (TFA; Sekhon et al., 2017) and data will be analysed through framework analysis (FA) so that data can be mapped onto this pre-existing theoretical framework. The use of the TFA to inform a topic guide and to structure FA has been

shown an effective way of collecting and analysing qualitative data on pilot interventions for pre-frailty (Western et al., 2023). A draft version of the topic guide for stroke survivor participants can be found in Appendix D. Development of the topic guides is ongoing, as discussions with PPI volunteers continue.

Quantitative Data

Stroke survivor's perspectives of the acceptability of the intervention will also be assessed using a questionnaire measure adapted from the 'generic TFA questionnaire' (Sekhon et al., 2022; Appendix E), which was produced by the team who developed the TFA itself (Sekhon et al., 2017). From this, descriptive data (mean ratings for each acceptability construct) can be collected. This scale has been used in several other studies investigating the acceptability of a new intervention, including with populations of pre-frail older adult memory clinic patients (Western et al., 2023). This questionnaire will be conducted via a pseudonymised online form, using Microsoft Forms, and distributed by email after the last session of the sCST intervention is completed and will need to be completed prior to the focus group discussions. Participants may be prompted by a further email to complete the form if response numbers are lower than expected in the lead-up to the focus groups.

Where possible, researchers will also keep an anonymous record of the number of participants identified as being eligible for the research so that a recruitment success percentage can be calculated. A percentage will also be calculated for stroke survivor participant retention rates; in other words, how many participants remain in the intervention for the full eight sessions. This will help to assess the feasibility of recruiting participants to take part in this research that uses this sCST intervention.

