Self-efficacy A participant's confidence that they can perform behaviour(s) required to participate in the intervention	How confident did you feel about [behaviour i.e. engaging with] [intervention]?															
	
 
 Very unconfident	Unconfident	No opinion	Confident	Very confident	
 
 1	2	3	4	5	
 
					Very unconfident	Unconfident	No opinion	Confident	Very confident	1	2	3	4	5	
Very unconfident	Unconfident	No opinion	Confident	Very confident												
1	2	3	4	5												
Opportunity costs The benefits, profits or values that would have to be given up to engage with the intervention	[Behaviour i.e. engaging in] [intervention] interfered with my other priorities															
	
 
 Strongly disagree	Disagree	No opinion	Agree	Strongly agree	
 
 1	2	3	4	5	
 
					Strongly disagree	Disagree	No opinion	Agree	Strongly agree	1	2	3	4	5	
Strongly disagree	Disagree	No opinion	Agree	Strongly agree												
1	2	3	4	5												
General acceptability	How acceptable was the [intervention] to you?					The general acceptability item has been included as in some instances, an overall acceptability item may be useful and to allow for researchers to explore which of the 7 TFA constructs influences/ drives participants' general acceptability judgment.										
	
 
 Completely unacceptable	Unacceptable	No opinion	Acceptable	Completely acceptable	
 
 1	2	3	4	5	
 
					Completely unacceptable	Unacceptable	No opinion	Acceptable	Completely acceptable	1	2	3	4	5	
Completely unacceptable	Unacceptable	No opinion	Acceptable	Completely acceptable												
1	2	3	4	5												

Note. From "Development of a theory-informed questionnaire to assess the acceptability of healthcare interventions" by M. Sekhon, M. Cartwright and J. J. Francis. Sekhon, 2017, *BMC Health Services Research*, 22(279), supplementary file 7(<https://doi.org/10.1186/s12913-022-07577-3>). CC BY 4.0 <http://creativecommons.org/licenses/by/4.0/>)

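### The survivor questionnaire is summarised only by mean ratings from about ten people, which can hide a dissenting minority; response counts, and n/N with intervals for the feasibility rates, should be added

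*Combined protocol and SAP*

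**What the plan says.** Under Measures and Data Collection (Quantitative Data), the protocol gives the questionnaire output as follows: "descriptive data (mean ratings for each acceptability construct) can be collected". The Analysis section obtains the degree of acceptability by "calculating the mean ratings for responses to each of the seven TFA constructs", together with "the mean rating for the general acceptability item (item 10), and the total mean rating of all items". No response counts, number answering, measure of spread or interval is mentioned.

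The Design section gives the questionnaire its purpose: "to quantify acceptability, helping to highlight areas of strength or weakness in intervention acceptability". Only stroke survivors complete it. On their number, the Participants section states: "The aim will be to recruit ten participants".

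Appendix E reproduces the generic instrument. Where response labels are shown, they run from 1 to 5 with 3 as *No opinion*. The general item, "How acceptable was the [intervention] to you", runs from *Completely unacceptable* to *Completely acceptable*.

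For feasibility, the number identified as eligible will be recorded where possible so that "a recruitment success percentage can be calculated". A second percentage gives the survivors who stay for all eight sessions. The Design section says these data will be reported descriptively. No interval is stated for either percentage.

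**The concern.** Averaging these codes treats having no view as lying halfway between rejection and endorsement, and lets strong approval cancel strong disapproval. With about ten respondents, two or three people who found the intervention unacceptable are a substantial share of the group. They are also the people whose answers bear most on the secondary question of how the intervention can be improved. A construct with a respectable mean could be read as a strength although several people rated it poorly. A mean near 3 could be read as lukewarm when opinion was split.

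The feasibility percentages are meant to inform the protocol of later research. A planner who sees only a percentage has neither the numbers behind it nor any sign of how imprecise it is.

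**Working it through.** **Inputs.** Ten survivors (Participants). Ten items: five constructs with one question, two constructs with two, and one general item, so 5 × 1 + 2 × 2 + 1 = 10 (Analysis), which agrees with the general item being number 10. Codes 1 to 5 (Appendix E). The protocol states no SD, expected rate or precision target. The sample of ten rests on group size, drop-out and manageability, so there is no precision figure of the plan's own to reproduce.

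**Step 1: what a mean can conceal.** Mean = sum of codes / 10. The table is for one item with ten answers, on an item such as item 10 where low codes are unfavourable.

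| Answers | Sum | Mean | Median | Rated 1 or 2 |
|---|---|---|---|---|
| ten 3s | 30 | 3.0 | 3 | 0 |
| five 1s, five 5s | 30 | 3.0 | 3 | 5 |
| ten 4s | 40 | 4.0 | 4 | 0 |
| six 5s, one 4, three 2s | 40 | 4.0 | 5 | 3 |
| eight 4s, two 5s | 42 | 4.2 | 4 | 0 |
| eight 5s, two 1s | 42 | 4.2 | 5 | 2 |

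The largest number k of unfavourable answers that a given mean allows follows from giving each of them a 2 and everyone else a 5. The sum can then be at most 2k + 5(10 − k) = 50 − 3k. For a mean of 4.0 this must be at least 40, so k ≤ 10/3 and at most 3 of 10 are unfavourable. For a mean of 4.2 it must be at least 42, so k ≤ 8/3 and at most 2 of 10.

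The median does not solve this: the first two rows share a median of 3. The counts separate every pair.

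**Step 2: sampling error of one item mean.** The 95% half-width is t(9; 0.975) × SD / √10 = 2.262 × SD / 3.162. The SD is my assumption: 0.5 gives 0.36 points, 1.0 gives 0.72 and 1.5 gives 1.07. This describes a single mean. A comparison of two constructs is paired within people and would depend on their correlation, which is not given.

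**Step 3: retention.** The exact (Clopper-Pearson) 95% limits for x of n are the 0.025 quantile of Beta(x, n − x + 1) and the 0.975 quantile of Beta(x + 1, n − x). With n = 10:
- 10/10: 69% to 100% (the lower limit is 0.025^(1/10) = 0.692)
- 8/10: 44% to 97%
- 7/10: 35% to 93%
- 5/10: 19% to 81%

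**Step 4: recruitment.** The denominator is the number identified as eligible, which the protocol does not predict. With ten enrolled and assumed eligible totals:
- 10/20: 27% to 73%
- 10/30: 17% to 53%
- 10/50: 10% to 34%
- 10/100: 5% to 18%

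**The case against.** A reader might infer that the whole study judges acceptability by means alone. The documents do not support that. Four focus groups, two of survivors and two of carers, are analysed by framework analysis with some open coding. The draft survivor topic guide (Appendix D) asks each person for one summarising word, then asks about dislikes, difficulties, negatives, barriers and changes. People who leave the intervention may still attend. The means-only summary is true of the questionnaire only, and dissent has another route to the surface. What remains is that the questionnaire is the individual, pseudonymised rating made before the group discussion. A focus group can reveal an objection, but it does not show how many of ten people rated the intervention unacceptable.

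A reader might also infer that the plan claims more certainty than it has. It does not: it calls the data descriptive, sets no threshold, tests nothing and does not propose to rank constructs. Nor do both feasibility rates rest on at most ten people. That fits retention if the target is not exceeded, but recruitment is divided by the number eligible.

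The intervals are also open to challenge. Exact limits assume independent outcomes and a fixed denominator. Retention comes from one weekly group, and the protocol itself anticipates clashes between members and difficult dynamics, so departures may be correlated and the limits too narrow. The eligible count is kept only where possible, and recruitment aims at ten. This objection stands as a caveat on the intervals; it is not a reason to leave a percentage bare.

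**Conclusion.** The point holds for the questionnaire summary and, as a lesser matter, for the two feasibility percentages. With ten answers, a mean of 4.0 is compatible with anything from no unfavourable ratings to three, and a mean of 3.0 with either no opinion from anyone or an even split between the extremes. That weakens the stated aim of showing where acceptability is strong or weak. The pattern results need only the 1-to-5 codes and ten respondents; with fewer respondents, each dissenter is a larger share.

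The retention intervals assume ten enrolled and independent outcomes. The recruitment intervals rest on eligible totals that I have assumed. This is a correction to reporting that should be made before analysis. It does not call into question the design, the sample size or the qualitative work.

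**What to change.** Amend the Analysis section and the Quantitative Data section to say:

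- For each of the ten items, report the number answering and the count in each response category, with *No opinion* shown as its own category, beside the mean. Keep the instrument's own scoring for the mean, so that no new rule is needed for *No opinion*.
- For item 10, also report the number choosing *Acceptable* or *Completely acceptable* out of those asked.
- Report recruitment as enrolled / identified eligible and retention as completed / enrolled. Give each as n/N with an exact 95% interval presented as an indication of imprecision. State that outcomes within one group may be correlated and that the eligible count may be incomplete.

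The cost is one extra table and a few lines of text. No further data, participants or thresholds are needed. The small downside is that the results will look less certain.

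### The acceptability questionnaire's total mean has no recoding rule, although on the generic anchors the opportunity-costs item runs opposite to six other items

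*Combined protocol and SAP*

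**What the plan says.** The Design section gives the questionnaire the task "to quantify acceptability, helping to highlight areas of strength or weakness in intervention acceptability". Under Measures and Data Collection, Quantitative Data, stroke survivors' views "will also be assessed using a questionnaire measure adapted from the" generic TFA questionnaire, from which "descriptive data (mean ratings for each acceptability construct) can be collected".

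The Analysis section sets the scoring rule: "the degree of acceptability will be calculated by calculating the mean ratings for responses to each of the seven TFA constructs", together with "the mean rating for the general acceptability item (item 10), and the total mean rating of all items". For the two constructs that have alternative questions (affective attitude and ethicality in Appendix E), "it has been decided that both of the suggested questions would be included in the acceptability questionnaire used in this study", because they were judged "different enough from one another that they would both be helpful to ask". The notes in Appendix E say that only one of each pair should be used. The plan does not say whether the two ratings in a pair are pooled into one construct mean.

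Appendix E prints numbered anchors from 1 to 5 for most items. None of these places says whether any item is reverse-scored before averaging.

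**The concern.** A mean across items can be read as a degree of acceptability only if a higher rating means the same thing on every item. On the generic anchors it does not. A participant who strongly agrees that taking part "interfered with my other priorities" scores 5, and that 5 raises the total just as a 5 for general acceptability does. Followed literally, the rule makes more interference look like more acceptability.

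Acceptability is the primary question of the stroke survivor arm (Research questions), and the questionnaire is its quantitative element. A total that is pulled toward the midpoint, or that hides a difference between two kinds of respondent, serves that purpose less well.

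**Working it through.** **Item count.** Seven constructs with one item each, plus one extra item for each of two constructs, plus the general item: 7 + 2 + 1 = 10. This agrees with the plan's numbering of the general acceptability item as item 10. All items is taken to mean these ten.

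**Directions visible in Appendix E.**

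| Item | Meaning of 5 |
|---|---|
| Affective attitude: like or dislike | favourable |
| Affective attitude: comfort | favourable |
| Ethicality: fairness | favourable |
| Intervention coherence | favourable |
| Self-efficacy | favourable |
| General acceptability (item 10) | favourable |
| Opportunity costs | unfavourable |
| Ethicality: moral or ethical consequences | unfavourable on its natural reading, but not explicitly negative |
| Burden (effort) | anchors not visible |
| Perceived effectiveness | anchors not visible |

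**Error from one adverse item.** Let A be the opportunity-costs rating. Recoding replaces A by 6 − A. The raw total minus the recoded total is (A − (6 − A))/10 = (2A − 6)/10 = (A − 3)/5.

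- A = 5: +0.4. A = 1: −0.4. These are the limits.
- The formula is linear, so it also holds for group means. A group mean of 2 gives −0.2 (total understated), and a group mean of 4 gives +0.2 (total overstated).

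This result does not depend on the direction of any other item.

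**Range for consistent respondents.** This step assumes that the other nine items all run favourably.

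- Most favourable throughout: (9 × 5 + 1)/10 = 4.6 instead of 5.
- Least favourable throughout: (9 × 1 + 5)/10 = 1.4 instead of 1.
- The span is 4.6 − 1.4 = 3.2 points instead of 4.0, or 80%.

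**Two respondents with the same raw total**, on the same assumption:

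- Nine items at 4 and interference at 1: raw (36 + 1)/10 = 3.7, recoded (36 + 5)/10 = 4.1.
- Six items at 4, three at 3 and interference at 4: raw (24 + 9 + 4)/10 = 3.7, recoded (24 + 9 + 2)/10 = 3.5.

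The raw total cannot tell them apart; the recoded totals differ by 0.6.

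**Conditional case: the consequences item is also adverse.** The errors add, so the total can be wrong by up to 0.4 + 0.4 = 0.8. If the two ethicality ratings are also pooled raw, with F for fairness and C for consequences, the construct mean is (F + C)/2. After recoding it is (F + 6 − C)/2.

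- F = 5, C = 1: raw 3.0, recoded 5.0.
- F = 1, C = 5: raw 3.0, recoded 1.0.

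Opposite respondents would then get the same raw ethicality score.

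**The case against.** The strongest reply is that the form to be scored is not in the documents. It is adapted from the generic one, and its wording or anchors may have been aligned. The plan does not rule out recoding either. A reader might therefore infer that the analysis will certainly mix directions; the documents do not support that. They support only the statement that the rule as written, applied to the generic anchors, does so. That part stands, because the plan mentions neither realignment nor recoding.

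Three other stronger readings also fail:

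- That the plan gives no item direction at all. Appendix E prints numbered anchors for most items; what is missing is the recoding rule.
- That opportunity costs opposes every other item, or that effort is a further reversed item. The anchors for effort and effectiveness are not visible in the text, so nothing follows about either.
- That the ethicality mean is certain to be uninformative. This needs the consequences item to be adverse, the pair to be pooled raw and the generic anchors to be kept. Asking both because they differ would also fit item-level reporting.

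It is also fair to say that little depends on the total. It is one of several summaries. The general acceptability mean is unaffected, and the single-item opportunity-costs mean can be read correctly once its direction is labelled. Focus groups analysed on the same framework run alongside. Item responses can still be recoded at analysis. This limits the harm, but it does not make the written rule correct.

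**Conclusion.** The point holds as a minor one. The Analysis section states an averaging rule that, on the generic anchors, combines one clearly adverse item with six clearly favourable ones. The firm size is an error in the total of at most 0.4 points, or 0.2 points at a group mean of 2 or 4. If the remaining items run favourably, the range for consistent respondents shrinks from 1–5 to 1.4–4.6. This rests on three assumptions: the adapted form keeps the generic anchors, the total covers ten items, and no unstated recoding is done.

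The 0.8-point total error and the uninformative ethicality mean are conditional, as set out above. A reader might go further and conclude that the study's answer on acceptability is unsafe. The documents do not support that: the ratings are descriptive, come from about ten stroke survivors, and feed no threshold or test.

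**What to change.** In the Analysis section, state the direction of each item on the final adapted form. Add that every item on which a higher rating means less acceptable is recoded as 6 minus the rating before any construct mean or total mean is taken. On the generic anchors this applies to opportunity costs and, on its natural reading, to the moral or ethical consequences item. Check the effort and effectiveness items against the final form. If the adapted form has already aligned the anchors, a sentence saying so is enough.

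Reporting the two ethicality items separately is optional once the direction is settled, but the plan should say whether they are pooled.

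The cost is two or three sentences. Item responses are collected anyway, so there are no new data and no change for participants.
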